## **6. BASELINE, EXPOSURE, AND DISPOSITION VARIABLES AND ANALYSES**

[Appendix A](#) provides a list of planned tables and listings. Sample data displays are included in a separate document.

### **6.1. Demographics, Baseline Characteristics, and Disease History**

#### **6.1.1. Demographics and Baseline Characteristics**

The following demographics will be summarized for the safety population: age, sex, race, ethnicity, weight, height, and BMI.

#### **6.1.2. Baseline Disease Characteristics and Disease History**

The following baseline disease characteristics and disease history will be summarized for the safety population and will include, but will not be limited to the following:

- Years since first onset (primary) wAIHA (< 2 years, 2-5 years, or > 5 years)
- Serological evidence
- Symptoms of wAIHA
- Number of hospitalizations due to hemolytic anemia in the year prior to screening
- Number of transfusions in the year prior to screening
- Failed therapies (no/yes)
- Any therapies contraindicated for the participant (no/yes)

#### **6.1.3. Prior Therapy**

Prior medication information for wAIHA will be used to identify other nonpredefined medication received by participants before enrollment into the study. Prior medication for wAIHA will be summarized by treatment group.

#### **6.1.4. Medical History**

Medical history will be summarized by treatment group. This summary will include the number and percentage of participants with medical history for each body SOC/PT as documented in the eCRF.

## **6.2. Disposition of Participant**

The number and percentage of participants who were enrolled, who were randomized (double-blind period only), who were treated, and who completed treatment for each period will be summarized for the safety populations.

## **6.3. Protocol Deviations**

Protocol deviations will be summarized and listed.

## **6.4. Exposure**

For participants in the safety population, exposure will be summarized descriptively for duration of treatment, average daily dose, and total dose. The treatment groups will be provided based on the actual treatment received (see Section [5.2](#)).

Duration of treatment with study drug is defined as the number of days from Day 1 to the date of last record of study drug administration. In addition, daily usage of prednisone (or equivalent) will be summarized using descriptive statistics.

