6.6. Treatment With Parsaclisib During Long-Term Extension

Participants may take a drug holiday one time during the long-term extension. Participants who take a drug holiday may be eligible to resume parsaclisib if they have worsening of wAIHA after the drug holiday. *Note*: Resuming treatment with parsaclisib is not an option for participants who permanently discontinue study treatment for criteria described in Section 7.1.1.

Participants may take a drug holiday during the long-term extension if they meet the following condition:

- Were clinically stable for at least 8 weeks and tolerating treatment before taking a drug holiday.
 - Clinically stable defined as hemoglobin ≥ 10 g/dL with an increase from baseline of ≥ 2 g/dL not attributed to rescue therapy and no worsening or new symptoms of wAIHA

Re-treatment with parsaclisib is available if the study remains open and the participant meets all of the following conditions:

• Experienced worsening of wAIHA defined as a continuing decline in absolute hemoglobin level, a > 1 g/dL decrease in hemoglobin from the prior assessment, or the participant develops new or worsening symptoms of wAIHA after the drug holiday.

AND

• In the opinion of the investigator, resuming treatment with parsaclisib would not pose a significant safety risk to the participant.

Participants will resume parsaclisib at the same dose level and frequency as when they last received parsaclisib. Re-treatment after a drug holiday is permitted one time. Participants will continue study treatment until any of the criteria for permanent discontinuation of study drug are met (see Section 7.1.1). Participants who permanently discontinue study treatment will enter the 12-week post-treatment follow-up visits scheduled every 4 weeks for 12 weeks after the last dose of study drug.

Note: Upon implementation of Protocol Amendment 2, participants receiving parsaclisib who permanently discontinue study drug will enter the post-treatment follow-up period for 1 visit (FUP1/EOS) approximately 4 weeks after the last dose of study drug.

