**Table 1: Objectives and Endpoints (Continued)**

### 3. STUDY DESIGN

[figure not shown]
This is a Phase 3, multicenter, randomized, double-blind, placebo-controlled study to evaluate the efficacy and safety of parsaclisib 2.5 mg QD compared with placebo over a 24-week double-blind treatment period followed by a 24-week open-label treatment period of parsaclisib. Participants may then continue to receive parsaclisib in a long-term extension period.

Participants will receive parsaclisib 2.5 mg QD or matching placebo QD for 24 weeks during the double-blind treatment period. All participants who complete the double-blind treatment period, tolerate study treatment, and (per investigator's opinion) may benefit from treatment, may remain in the study for an additional 24-week, open-label treatment period in which they will receive parsaclisib administered at the same dose and schedule as in the double-blind treatment period.

All participants who complete the open-label treatment period, tolerate study treatment, and (per investigator's opinion) may benefit from continued treatment, may enter into the long-term extension. Parsaclisib will be administered at the same dose and schedule as in the open-label treatment period. During the long-term extension, participants may take a drug holiday one time with the option for re-treatment, should they experience worsening of wAIHA during the drug holiday.

The study schema is shown below in [Figure 1](#). All participants will have follow-up assessments 12 weeks after the last dose of study drug.

**Figure 1:** Study Design Schema

ICF = informed consent form.

a Hemoglobin, at screening, as determined by local laboratory (< 9 g/dL or  $\geq$  9 g/dL) and corticosteroid (prednisone or equivalent) dose at screening ( $\leq$  20 mg/day vs  $>$  20 mg/day).

b The primary analysis will be conducted when the last randomized participant has completed the 24-week, double-blind treatment period.

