### 9.1. General Considerations

Analyses in this section will be provided for the safety population. Treatment groups will be provided based on the actual treatment received (see Section 5.2). For participants who cross over treatments, the date of first dose is treatment-specific; the end date will be either 30 days after the date of the last dose of this treatment or the date of the first dose in the next treatment, whichever comes first. Analysis of AEs will be limited to TEAEs, but data listings will include all AEs regardless of their timing in relation to study drug administration. Summary tables may be replaced with listings when appropriate. For instance, an AE frequency table may be replaced with a listing if it only contains a few unique PTs reported on relatively few participants.

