### 9.2. Adverse Events

#### 9.2.1. Adverse Event Definitions

A TEAE is any AE either reported for the first time or worsening of a pre-existing event after first dose of study drug and within 30 days of the last dose of study drug. Analysis of AEs (as discussed below) will be limited to TEAEs, but data listings will include all AEs regardless of their timing in relation to study drug dose administration.

Adverse events will be tabulated by MedDRA PT and SOC. Severity of AEs will be graded using the National Cancer Institute CTCAE v5. The CTCAE reporting guidelines and grading details are available on the Cancer Therapy Evaluation Program website.

The subset of AEs considered by the investigator to be related to study drug will be considered treatment-related AEs. If the investigator does not specify the relationship of the AE to study drug, the AE will be considered to be treatment-related. The incidence of AEs and treatment-related AEs will be tabulated. Serious AEs will also be tabulated.

Any missing onset date, causality, or severity must be queried for resolution. Unresolved missing causality and severity will be handled according to the following rules:

- An unresolved missing causality will be considered treatment-related.
- An unresolved missing severity will be identified as an unknown severity.

For purposes of analysis, all AEs will be considered TEAEs unless the AE can unequivocally be defined as not treatment-emergent.

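### For participants who resume parsaclisib after a drug holiday, SAP 6.4 counts the off-drug days as treatment duration, and SAP 9.2.1 counts late off-drug AEs that it would exclude had they not resumed

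*SAP*

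**What the plan says.** - **Holiday.** Protocol 6.6 states: "Participants may take a drug holiday one time during the long-term extension". It gives no maximum length. It also states: "Re-treatment with parsaclisib is available if the study remains open and the participant meets all of the following conditions". Those conditions are worsening of wAIHA after the holiday and the investigator's opinion that resuming poses no significant safety risk.
- **The SAP knows of it.** In its design description (SAP 3), "participants may take a drug holiday one time with the option for re-treatment". SAP 6.4, 9.1 and 9.2.1 do not mention the holiday again.
- **Exposure.** Under SAP 6.4, "exposure will be summarized descriptively for duration of treatment, average daily dose, and total dose". Duration is "defined as the number of days from Day 1 to the date of last record of study drug administration". No denominator is given for average daily dose.
- **TEAE window.** Under SAP 9.2.1 an AE is treatment-emergent if it first occurs or worsens "after first dose of study drug and within 30 days of the last dose of study drug". A default follows: "all AEs will be considered TEAEs unless the AE can unequivocally be defined as not treatment-emergent".
- **The only segmenting rule.** SAP 9.1 deals with participants who cross over treatments. For them the first-dose date is specific to each treatment, and "the end date will be either 30 days after the date of the last dose of this treatment" or the first dose of the next treatment, whichever is earlier.

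**The concern.** Both SAP rules assume one unbroken course of treatment, but the protocol provides for a gap. When drug is resumed, the last recorded dose falls in the second course, so every day of the gap lies between Day 1 and the last dose.

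Two things follow. First, duration of treatment includes time off drug. Second, two participants equally far from their last pre-holiday dose are treated differently. An AE on off-drug day 60 is a parsaclisib TEAE if the participant later resumes and is not one if the participant does not. Later events decide which rule applies: relapse, the study still being open, and the investigator's safety judgment. A safety definition should not depend on what happens after the event it classifies.

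What is at stake is the meaning of the duration column in the exposure table and the attribution of a few late off-drug events to parsaclisib.

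**Working it through.** The documents give no figure to reproduce for this point; it rests on definitions and day counts.

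**Inputs from the documents**
- Duration rule: SAP 6.4.
- TEAE window, 30 days after last dose: SAP 9.2.1.
- Holiday allowed once, no maximum, resumption conditional: Protocol 6.6.
- 13 participants randomized and treated: SAP 1.

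**Assumed inputs**
- The documents give no holiday lengths, so H (holiday days) runs from 14 to 336.
- A = 392 on-drug days before the holiday (56 weeks).
- B = 56 or 168 on-drug days after it (8 or 24 weeks).

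**Formulas**
- Duration under SAP 6.4, resumer: A + H + B. On-drug days: A + B. Overstatement: H / (A + B).
- Duration under SAP 6.4, non-resumer: A. The holiday adds nothing, because the last dose record precedes it.
- Off-drug days inside the TEAE window: H for a resumer, min(H, 30) for a non-resumer. Difference: max(0, H − 30).

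**Results**

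| H | Duration, B = 56 (448 on drug) | Excess | Duration, B = 168 (560 on drug) | Excess | Window difference |
|---|---|---|---|---|---|
| 14 | 462 | 3.1% | 574 | 2.5% | 0 |
| 30 | 478 | 6.7% | 590 | 5.4% | 0 |
| 56 | 504 | 12.5% | 616 | 10.0% | 26 |
| 84 | 532 | 18.8% | 644 | 15.0% | 54 |
| 168 | 616 | 37.5% | 728 | 30.0% | 138 |
| 336 | 784 | 75.0% | 896 | 60.0% | 306 |

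Worked row: 392 + 84 + 168 = 644; 84 / 560 = 15.0%; 84 − 30 = 54.

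**Calendar check.** Protocol 2.2 dates the study start to MAR 2022. If a first participant was dosed on 1 MAR 2022, Week 48 (336 days) falls on 31 JAN 2023, so a holiday could begin before the SAP of 17 JAN 2024. That SAP date is day 687 counted from 1 MAR 2022. The rows at 728, 784 and 896 days would run past it, so the shorter rows are the realistic ones.

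**Other exposure measures**
- Total dose is unaffected.
- Compliance (SAP 6.5) uses doses prescribed as its denominator, so holiday days need not enter it.
- Average daily dose depends on its unstated denominator. If that is duration, with every on-drug day at 2.5 mg, A = 392, B = 168 and H = 168, it reads 2.5 × 560 / 728 = 1.92 mg. If it is on-drug days, it reads 2.5 mg.

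**Does another SAP rule close the gap?** The SAP 9.1 rule applies at a change of treatment, and parsaclisib before and after a holiday is the same treatment. The SAP 9.2.1 default does not equalize the two cases either: an AE with a known onset on day 60 in a non-resumer is unequivocally outside the window.

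**The case against.** The strongest case on the other side is that little depends on this.

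- **Small and descriptive.** There are 13 treated participants. The AE summaries in SAP 9.2.2 are numbers and percentages of participants with no exposure adjustment, so a longer duration feeds no listed AE rate.
- **Nothing is lost.** SAP 9.1 and 9.2.1 list all AEs whatever their timing, and Listing 1.5 covers exposure and compliance.
- **The relapse is not an AE.** Protocol 9.1 excludes disease worsening from AE reporting, so the event that triggers re-treatment should not itself enter the window.
- **The SAP is inclusive by design.** Keeping a resumer's off-drug AEs fits the default rule, and closing the window would remove events from the parsaclisib TEAE tables.
- **The scenario is narrow.** It needs entry to the long-term extension, 8 weeks of clinical stability, then worsening while the study is still open, with termination decided on 17 APR 2023.

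All of this stands and limits the importance of the point. None of it supplies a rule for the gap or makes off-drug days treatment time. The inclusive default is a good reason to prefer flagging over removal.

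A reader might also infer three stronger things that the documents do not support:
- That off-drug AEs count only for participants who resume. The first 30 off-drug days count for everyone; the asymmetry starts on day 31.
- That every holiday inflates duration. It does so only when drug is resumed.
- That average daily dose will look like a dose reduction. That needs duration as the denominator, which SAP 6.4 does not state. SAP Appendix A refers to standard safety tables that were not supplied.

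**Conclusion.** The point holds for participants who resume after a holiday. For them SAP 6.4 counts all H off-drug days as duration of treatment, and SAP 9.2.1 counts AEs from off-drug day 31 onward that it would exclude for a non-resumer. Because resumption requires worsening of wAIHA, the difference depends on outcome.

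For assumed holidays of 56 to 168 days, the window difference is 26 to 138 days. The excess duration is 10% to 30% with 560 on-drug days and 12.5% to 37.5% with 448. Holidays of 30 days or less create no TEAE difference, though a resumer's duration is still overstated.

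This is a minor definitional gap. Reclassifying one participant moves a percentage over all 13 by 1/13 = 7.7 points, and by more within a single treatment column. The documents do not say whether anyone took a holiday, so they do not support a claim that the reported results are distorted.

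**What to change.** - **SAP 6.4.** Define duration of treatment net of holiday days, or report gross and net side by side. State that average daily dose is computed over on-drug days.
- **SAP 9.1 and 9.2.1.** Choose and state one convention. Either apply the 30-day window to each dosing segment, closing it 30 days after the last pre-holiday dose and reopening it at re-treatment; or keep the inclusive window, but flag and tabulate separately AEs with onset more than 30 days after the last pre-holiday dose and before re-treatment. The second option suits the SAP's inclusive default better.
- **If no one took a holiday,** one sentence saying so in the study report settles the matter.

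The cost is a few lines of SAP text and minor programming from dosing dates already collected. If the window is closed by segment, a few off-drug events could move from the TEAE tables to the listings. No clinical rule changes.

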## **6.5. Study Drug Compliance**

For the participants in the safety population, overall compliance (%) for study drug administration will be calculated as follows:

$$\text{Compliance (\%)} = 100 \times [\text{total dose taken}] / [\text{total intended dose}]$$

The total number of intended doses defined as the number of dose prescribed.

## **6.6. Prior and Concomitant Medication**

Prior medications and concomitant medications will be coded using the WHO Drug Dictionary. The number and percentage of participants in the safety population for each prior and concomitant medication will be summarized by WHO drug class and WHO drug preferred name.

Prior and concomitant medications will also be summarized (and listed) by treatment group.

## **7. EFFICACY**

With limited participants enrolled in each treatment group, as well as the option for early crossover to parsaclisib, the statistical analyses, as related to efficacy and defined by the Protocol, will not be applicable; as a result, no p-values will be provided and no multiple adjustment will be made.

[figure not shown]
### **7.1. Efficacy Hypotheses**

Not applicable.

### **7.2. Analysis of the Primary Efficacy Parameters**

The primary endpoint will be defined as a success if the proportion of participants attain a durable hemoglobin response  $\geq 10$  g/dL with an increase from baseline of  $\geq 2$  g/dL. The key secondary endpoint will be considered a success if the proportion of participants have a  $\geq 3$ -point increase from baseline in FACIT-F score at Week 24.

For primary and key secondary endpoints, postbaseline visits will be summarized by treatment received on Day 1 of the study; the visits will use descriptive statistics.

## 9. SAFETY AND TOLERABILITY

[Appendix A](#) provides a list of data displays. Sample data displays will be included in a separate document.

### 9.1. General Considerations

Analyses in this section will be provided for the safety population. Treatment groups will be provided based on the actual treatment received (see Section 5.2). For participants who cross over treatments, the date of first dose is treatment-specific; the end date will be either 30 days after the date of the last dose of this treatment or the date of the first dose in the next treatment, whichever comes first. Analysis of AEs will be limited to TEAEs, but data listings will include all AEs regardless of their timing in relation to study drug administration. Summary tables may be replaced with listings when appropriate. For instance, an AE frequency table may be replaced with a listing if it only contains a few unique PTs reported on relatively few participants.

### 9.2. Adverse Events

#### 9.2.1. Adverse Event Definitions

A TEAE is any AE either reported for the first time or worsening of a pre-existing event after first dose of study drug and within 30 days of the last dose of study drug. Analysis of AEs (as discussed below) will be limited to TEAEs, but data listings will include all AEs regardless of their timing in relation to study drug dose administration.

Adverse events will be tabulated by MedDRA PT and SOC. Severity of AEs will be graded using the National Cancer Institute CTCAE v5. The CTCAE reporting guidelines and grading details are available on the Cancer Therapy Evaluation Program website.

The subset of AEs considered by the investigator to be related to study drug will be considered treatment-related AEs. If the investigator does not specify the relationship of the AE to study drug, the AE will be considered to be treatment-related. The incidence of AEs and treatment-related AEs will be tabulated. Serious AEs will also be tabulated.

Any missing onset date, causality, or severity must be queried for resolution. Unresolved missing causality and severity will be handled according to the following rules:

- An unresolved missing causality will be considered treatment-related.
- An unresolved missing severity will be identified as an unknown severity.

For purposes of analysis, all AEs will be considered TEAEs unless the AE can unequivocally be defined as not treatment-emergent.

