Visit Day (Range)	W26 ± 3 d	W28 ± 5 d	W30 ± 5 d	W32 ± 5 d	W36 ± 5 d	W40 ± 5 d	W44 ± 5 d	EOT2 W48 ± 5 d	FUP1a/ EOS	FUP2 ^b	FUP3 ^b	Notes and Protocol Section
Efficacy assessments	1	ı		1								
Hematology	X*	X	X*	X	X	X	X	X	X	X	X	*No longer required upon implementation of Protocol Amendment 2.
DAT								X				Section 8.2.1 and Section 8.4.5
PRO and clinical outcome asses	sments (Note: U	pon imp	olementa	tion of P	rotocol A	mendme	nt 2, the l	PROs note	d herein	will no lo	
FACIT-F scale		X		X		X		X			X	Should be completed before any other assessments. Must be completed before all other PRO assessments. Section 8.3.1

Table 4: Schedule of Activities (Open-Label) (Continued)

			0	pen-Lab	el Treat	ment				st-Treatm Follow-Uj		
	W26	W28	W30	W32	W36	W40	W44	EOT2 W48	FUP1a/	THE	ELIDAL	
Visit Day (Range) PRO and clinical outcome assess	±3 d	±5d	± 5 d	±5d	±5d	±5d	±5d	±5d	EOS	FUP2b	FUP3b	Notes and Protocol Section
6MWT	sments (continue	u) (Note	: Ороп	пприете	псистоп о	Protoco	X	ment 2, the	e PROS III	X	Vital signs should be conducted pre- and post-test. 6MWT must be performed after all other PRO assessments are completed. Section 8.3.2
Laboratory assessments ^c D-dimer		X		X	X		X	X				Section 8.4.5
Serum pregnancy								X			X	WOCBP only. Section 8.4.5.1
Urine pregnancy		X		X		X			X	X		WOCBP only. Section 8.4.5.1
Serum chemistry CMV		X		X	X X*	X	X	X	X	X	X	Section 8.4.5 *Monitor as clinically indicated

a Only required for participants receiving parsaclisib; post-treatment follow-up visit to be conducted 4 weeks (± 5 days) after EOT visit (or after the last dose of study drug if the EOT visit was not performed).

^b No longer required upon implementation of Protocol Amendment 2.

^c Fasting is not required for central laboratory assessments.

 Table 5:
 Schedule of Activities (Long-Term Extension)

		Long-Tern			
Visit Day (Range)	W56 (± 7 d)	Every 8 Weeks (± 7 d)	Every 16 Weeks (± 7 d)	EOT3a	Notes and Protocol Section
In-office visit	X	X		X	
Administrative procedures					·
Contact IRT	X	X		X	Section 8.1.3
Prior/concomitant medications	X	X		X	Section 6.7
Distribute reminder cards	X	X		X	Section 8.1.4
Dispense study drug	X	X			Section 6.1 and Section 8.1.3
Study drug return, accountability and compliance assessment	X	X		X	Section 6.4
Prophylactic treatment for PJP		As prescribed by the inve	estigator throughout study		Section 6.7.1.1
Healthcare resource utilization	X		X	X	Section 8.3.8
Safety assessments		-	1		
Comprehensive physical examination				X	Section 8.4.2

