8.4. Safety Assessments

8.4.1. Adverse Events

Adverse events will be monitored from the time the participant signs the ICF until at least 12 weeks after the last dose of study drug. Adverse events for enrolled participants that begin or worsen after informed consent should be recorded on the Adverse Events Form in the eCRF regardless of the assumption of a causal relationship with the study drug. Conditions that were already present at the time of informed consent should be recorded on the Medical History Form in the eCRF. Adverse events (including laboratory abnormalities that constitute AEs) should be described using a diagnosis whenever possible rather than by individual underlying signs and symptoms.

Adverse events will be reported by the participant (or, when appropriate, by a caregiver, surrogate, or the participant's legally authorized representative). The investigator and any qualified designees are responsible for detecting, documenting, and recording events that meet the definition of an AE or SAE and remain responsible for following-up on AEs that are serious, that are considered related to the study drug/procedures, or that caused the participant to discontinue the study drug. Care will be taken not to introduce bias when detecting AEs and/or SAEs. Open-ended and nonleading verbal questioning of the participant, such as "How are you feeling?", is the preferred method to inquire about AE occurrences. Adverse events may also be detected when they are volunteered by the participant during the screening process or between visits or through physical examinations, laboratory tests, or other assessments. The definition, reporting, and recording requirements for AEs are described in Section 9.

All SAEs will be reported to the sponsor or designee within 24 hours (immediately in Germany). The investigator will submit any updated SAE data to the sponsor within 24 hours (immediately in Germany) of it being available.

After the initial AE/SAE report, the investigator is required to proactively follow each participant at subsequent visits/contacts. All SAEs will be followed until resolution, stabilization, the event is otherwise explained, or the participant is lost to follow-up (as defined in Section 7.3).

At remote visits, adverse events will also be assessed via a phone call conducted by the study site, except for countries where remote visits are not permitted by local laws and/or regulations (see Table 3, Table 4, and Table 5).

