8.10. Post-Treatment Follow-Up

The post-treatment follow-up period, comprised of 3 visits (one every 4 weeks; FUP1, FUP2, and FUP3), is the interval between the EOT visit and the scheduled follow-up visits, which should occur at a minimum of 30 days to 84 days after the EOT visit (or after the last dose of study drug if the EOT visit was not performed). The FUP1 and FUP2 visits will be conducted remotely, except for countries where remote visits are not permitted by local laws and/or regulations. Adverse events and SAEs must be reported up until 1) at least 84 days after the last dose of study drug or 2) until toxicities resolve, return to baseline, or are deemed irreversible, whichever is longer. Reasonable efforts should be made to have the participant return for the FUP3 visit and report any AEs that may occur during this period. In exceptional cases when the participant cannot return to the site for the FUP3 visit, the participant should be contacted by telephone for assessment of AEs and SAEs and the site should properly document the contact.

Note: Upon implementation of Protocol Amendment 2:

- Participants receiving parsaclisib who permanently discontinue study drug will enter the post-treatment follow-up period for 1 visit approximately 4 weeks after the last dose of study drug.
- Participants receiving placebo who permanently discontinue study drug will no longer be required to enter the post-treatment follow-up period and will perform EOT/EOS upon discontinuation of treatment.

9. ADVERSE EVENTS: DEFINITIONS AND PROCEDURES FOR RECORDING, EVALUATING, FOLLOW-UP, AND REPORTING

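### After Amendment 2 only parsaclisib stoppers have a scheduled contact in the 30 days after the last dose, yet the SAP counts TEAEs over those 30 days in every group

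*SAP*

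**What the plan says.** **TEAE window.** SAP 9.2.1 includes events "after first dose of study drug and within 30 days of the last dose of study drug". SAP 9.1 makes the dates treatment-specific for participants who cross over: "the end date will be either 30 days after the date of the last dose of this treatment or the date of the first dose" of the next treatment, whichever is earlier. SAP 5.2 sets three groups for adverse events (placebo, placebo to parsaclisib, and parsaclisib), and SAP 9.2.2 tabulates any, serious, Grade 3 or higher, related and fatal TEAEs by group.

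**Follow-up after Amendment 2.** Protocol 8.10 says of placebo: "Participants receiving placebo who permanently discontinue study drug will no longer be required to enter the post-treatment follow-up period". They have EOT/EOS on stopping. Participants who stop parsaclisib, by contrast, "will enter the post-treatment follow-up period for 1 visit approximately 4 weeks after the last dose of study drug". The footnote to Table 4 in Protocol Section 1 says of FUP1: "Only required for participants receiving parsaclisib; post-treatment follow-up visit to be conducted 4 weeks (± 5 days) after EOT visit". Table 4 schedules AE assessment, physical examination, vital signs, hematology and chemistry at FUP1, and marks FUP2 and FUP3 as no longer required.

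**Text that does not match the reduced visits.** SAP 2.1 states that the plan is based on Amendment 2, but SAP Section 3 says: "All participants will have follow-up assessments 12 weeks after the last dose of study drug". Protocol 8.4.1 says: "Adverse events will be monitored from the time the participant signs the ICF until at least 12 weeks after the last dose of study drug". Protocol 8.10 keeps AE and SAE reporting to at least 84 days after the last dose. Protocol 9.4 keeps SAE reporting through the last safety visit or at least 30 to 35 days. None of these is limited by arm.

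**The concern.** A common TEAE window gives a fair comparison only if events inside it are looked for in the same way in each group. Here the last 30 days of the window contain a scheduled visit with laboratory tests in one group and no scheduled contact in the other. Events can follow the decision to stop treatment, and laboratory abnormalities in particular need a visit to be found. The expected direction is an apparent excess of TEAEs on parsaclisib with no drug effect behind it.

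This is separate from the longer open-label exposure on parsaclisib. Restricting the tables to the double-blind period would not remove it, because the difference lies after the last dose. Dividing by dosing days would not remove it either, because the post-dose events would still enter the numerator mainly on parsaclisib.

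**Working it through.** The documents give no figure for this point, so there is none to reproduce. The check sets the windows side by side and then sizes the gap under stated assumptions.

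**1. Scheduled contact inside the 30 post-dose days, after Amendment 2**

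| Participant | Scheduled contact after the last dose | Part of the 30 days covered |
|---|---|---|
| Stops parsaclisib | FUP1 at 28 ± 5 days (day 23 to 33) | 23/30 = 77%; 28/30 = 93%; 100% from day 30 |
| Stops placebo, no crossover | None after EOT/EOS | No scheduled visit |
| Placebo, crosses over directly | Continues with open-label visits | Placebo window closes at the first parsaclisib dose |

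Days are counted from the EOT visit, taken here to fall on the day of the last dose.

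**2. Share of a placebo stopper's TEAE window that has no scheduled contact**, 30/(T + 30), with T the days on treatment:
- Week 8: 30/86 = 35%
- Week 12: 30/114 = 26%
- Week 24: 30/198 = 15%

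**3. Illustrative size per stopper.** Assumptions: the same constant hazard in both groups, a 50% risk of any TEAE over 168 days, FUP1 at day 28, and no placebo event reported after EOT. The documents supply none of these except the day-28 visit. The risk of at least one captured TEAE over t days is 1 − 0.5^(t/168).

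| Stop at | Placebo, to EOT | Parsaclisib, to FUP1 | Difference |
|---|---|---|---|
| Week 8 | 56 days: 20.6% | 84 days: 29.3% | 8.7 points |
| Week 12 | 84 days: 29.3% | 112 days: 37.0% | 7.7 points |
| Week 24 | 168 days: 50.0% | 196 days: 55.5% | 5.5 points |

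One hazard is used throughout. Resetting the placebo risk to 50% at each stopping time would give the Week 8 case three times the Week 24 hazard and inflate the early differences.

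**4. Range over the assumed risk**, replacing 0.5 by 1 − p, where p is the risk over 168 days:
- p = 30%: Week 8, 16.3 − 11.2 = 5.1 points; Week 24, 34.0 − 30.0 = 4.0 points
- p = 60%: Week 8, 36.8 − 26.3 = about 10.4 points from unrounded values; Week 24, 65.7 − 60.0 = 5.7 points
- p = 90%: Week 8, 68.4 − 53.6 = 14.8 points; Week 24, 93.2 − 90.0 = 3.2 points

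**5. From stopper to column.** These are differences per stopper. If k of n participants in the placebo column are affected, the column percentage is lowered by k/n times the per-stopper difference. Neither k nor n is given. SAP Section 1 reports 13 participants randomized and dosed. The ratio was 1:1 before Amendment 1 and 2:1 after it, so placebo is probably between 13/3 = 4.3 and 13/2 = 6.5 people, an assumption about how enrollment fell across the two periods. In a column of 4 to 6, one undetected participant with an event moves the percentage by 1/4 = 25 to 1/6 = 17 points.

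**The case against.** A reader might infer that post-dose events are sought in one arm only, that ascertainment on placebo is zero, and that the placebo rate is therefore not a valid comparator. The documents do not support this, for four reasons, all of which stand.

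- **The duties remain.** Amendment 2 removes a visit. It does not remove the monitoring in Protocol 8.4.1, the reporting in 8.10 and 9.4, or the rule in 7.1.2 that discontinued participants are followed for safety until the follow-up visit or until drug-related toxicities resolve. As written, a placebo event on day 15 after stopping should still be reported. What is lost is the scheduled occasion for finding it.
- **The affected subset is narrow.** The rule applies only upon implementation of Amendment 2, dated 10 May 2023; the study began in March 2022. Earlier stoppers in both groups were under the 12-week, 3-visit follow-up. Direct crossovers have no unvisited post-dose time. The subset that remains could be empty.
- **No inference is planned.** SAP 11.1 provides no p-values and no statistical comparisons, listings include all AEs regardless of timing, and sparse tables may become listings.
- **Cutting the main table would have a cost.** Moving post-dose parsaclisib events, including serious ones, out of the main TEAE table would be hard to defend when the protocol itself raises late-onset events and serious infections. Bias against the drug is also the cautious direction for safety.

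It may also be said that SAP 3.4 sends the reader to Amendment 2 for all schedules, so the SAP Section 3 sentence is only editorial. Taken alone, it is. What does not fall away is that a reporting duty without a visit does not give the same detection as a visit with laboratory tests, and the SAP does not say that follow-up differs by group.

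**Conclusion.** The concern holds as unequal detection in the post-dose part of the TEAE window, not as absent detection on placebo. The arm-specific visit rule and the common 30-day window are explicit in the text, so the direction is clear: post-dose events are more likely to be found on parsaclisib.

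The size is uncertain and probably small overall. The figure of about 5.5 to 8.7 points is per stopper and rests on an assumed 50% risk over 168 days. It is an upper bound in that placebo reporting after EOT is set to zero, which the retained duties contradict. It must not be read as an arm-level bias. The number of affected participants is not stated, and the output is descriptive. The point is worth acting on because the remedy uses data already held and the columns are so small that one event is visible in a percentage.

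**What to change.** 1. **SAP 9.1 and 9.2.1:** keep the 30-day TEAE tables. Add an on-treatment version of the overall, serious and Grade 3 or higher summaries, closing the window at the same point in each group: the last dose, or the EOT visit if later. For crossovers, keep the existing cut at the first parsaclisib dose.
2. **Tables and listings:** flag events after that point up to 30 days as post-treatment. Footnote that, after Amendment 2, only parsaclisib participants had a scheduled follow-up visit.
3. **SAP Section 3:** align the follow-up sentence with Amendment 2.
4. **Protocol 8.4.1, 8.10 and 9.4:** reconcile the 12-week, 84-day and 30-to-35-day AE and SAE periods with the reduced visits, and state what was actually applied to placebo participants who stopped.

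The cost is a few extra tables and one date derivation. No new data are needed and no parsaclisib event leaves the main tables. The change does not remove the separate imbalance from open-label time in the parsaclisib column.
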